6.1 Population and treatment
6.1.1 Population
6.1.2 Carfilzomib treatment
6.1.3 Sample size
6.1.4 History record11
6.2 Functional and structural assessment of the vasculature12
6.2.1 Assessment of arterial stiffness
Arterial stiffness in the aorta by measurement of pulse wave velocity (PWV)
Central blood pressures and reflected waves in the aorta
6.2.2 Endothelial function by ultrasound measurement of endothelium-dependent flow- mediated dilatation (FMD)

6.2.3 Carotid and Femoral Intima-Media Thickness (IMT)	13
6.2.4 Ankle Brachial Index (ABI)	14
6.2.5 24-hour Ambulatory Blood Pressure Monitoring (ABPM)	14
6.3 Cardiac Ultrasonography	14
6.4 Study of Proteasome activity	15
Blood collection – isolation of cells	15
RNA extraction and Quantitative Real-Time PCR (Q-RT-PCR) analyses	15
Measurement of proteasome peptidase activities in PBMCs and RBCs extracts	16
Preparation of cell protein extracts, immunoblotting analyses and detection of prote carbonyl groups	
Confocal microscopy	16
Measurement of Reactive Oxygen Species (ROS)	16
6.5 Measurement of circulating cardiac and vascular inflammatory biomarkers	16
7. Timelines of the study	17
8. Data presentation and statistical analysis	17
9. Safety reporting	18
9.1 Adverse Events Definitions	18
9.2 Causality	18
9.3 Definition of Adverse Drug Reactions (ADRs)	19
9.3.1 Definition of Serious Adverse Events	19
9.3.2 Definition of Serious Adverse Drug Reactions (SADRs)	19
9.3.3 Definition of Special Situations	19
9.4 Adverse Events Reporting Procedures	20
9.4 Serious Adverse Event Reporting and Documentation Requirements	20
10. References	21

Study Synopsis

Study Title:	An observational study of Cardiovascular complications of Carfilzomib treatment in clinical practice.						
Methods:	This is an, observational, non interventional, study in patients with relapsed or refractory myeloma treated with carfilzomib (CFZ), according to the approved indications. Patients will be evaluated prospectively for different parameters of vascular function, blood pressure and cardiac function in conjunction with studies of proteasome inhibition and function. The aim of this study is to provide insights into the effects of carfilzomib on vascular function and the mechanisms of UPS inhibition on cardiovascular complications of proteasome inhibitors.						
Objectives:	 Primary to describe cardiovascular complications associated with the use of carfilzomib and investigate the role of the UPS inhibition, in patients treated with carfilzomib and dexametahsone, on atheromatosis and vascular inflammation and function 						
	 Secondary to outline the clinical significance of carfilzomib toxicity in hemodynamic parameters and cardiovascular function and vascular structure 						
Endpoints	 Primary Changes in hemodynamic markers (peripheral and aortic office blood pressure and 24 hour ambulatory BP monitoring parameters) and in peripheral vascular function (endothelial function, arterial stiffness, arterial wave reflections) before, during and after study drug administration 						
	 Secondary Changes in subclinical atherosclerosis markers (carotid intima-media thickness and vascular wall and plaque echogenicity) changes in markers of cardiac function (ejection fraction, 						

Population:	 systolic and diastolic strain and strain rate) changes in circulating cardiac and vascular inflammatory biomarkers (NtproBNP, cTnT, C-reactive protein, interleukin 6, vascular cell and intercellular adhesion molecule-1, E-selectin, and monocyte chemoattractant protein-1) before and after study drug administration Patients with relapsed or refractory myeloma treated with carfilzomib as per approved indications
Phase:	This is an observational, non interventional, prospective study
Number of Sites:	This is a single center study
Description of Study assessments:	Patients with an indication to receive carfilzomib & dexamethasone will be treated according to approved dose and schedule
	A. Vascular studies: Vascular measurements will be performed at baseline before and after dexamethasone, before and after CFZ administration, 2 hours and 24 hours after CFZ administration. These measurements will be repeated on days 8,9,15 and 16 of cycle 1, on days 1,2 of cycles 2 and 3 and days 1,2,15 and 16 of cycle 6 or earlier if the patient develops progression of disease. Vascular measurements include assessment of arterial stiffness, arterial wave reflections, subclinical carotid and femoral atherosclerosis and carotid plaque composition, using non-invasive well-validated techniques. Blood pressure will be evaluated using 24h hour ambulatory monitoring at baseline and on days 1 and 8 of cycle 1 and at the beginning of cycles 2, 3 and 6.
	B. In vitro studies: In parallel and at each time point, the activity of UPS and intracellular levels of ubiquitin conjugates will be measured in peripheral blood mononuclear cells (PBMCs) and red blood cells (RBCs) using enzymatic proteasome activity assays and western blot techniques, respectively.
Study Duration:	2 years

1. Background

Proteasome inhibitors (PI) have emerged as highly effective drugs on the treatment of multiple myeloma (MM) and actually they are currently standard of care at all stages of the disease. After the initial approval of bortezomib, the first-in-class PI, by the U.S. Food and Drug Administration (FDA) on 2003 for the treatment of relapsed/refractory MM, the role of proteasome has been extensively explored and the ubiquitin-proteasome pathway has been clearly documented as a major target for myeloma therapy. "Second" generation PIs, such as carfilzomib (CFZ), were developed with improved efficacy and safety profiles, expanding the therapeutic spectrum for patients with progressive MM. Carfilzomib is an epoxyketone proteasome inhibitor that binds selectively and irreversibly to the β- subunit of the 20S proteasome and more specifically targets the chymotrypsin catalytic subunit. However in the clinical studies of carfilzomib (either single agent or in combination with other agents) a low but constant signal of potential cardiotoxicity or hypertension, have been observed, but the mechanisms have not been studied prospectively and in depth (1). In the ENDEAVOR study a subgroup of patients followed prospectively with cardiac echocardiography did not reveal either prognostic or predictive factors associated with the risk of cardiotoxicity or hypertension. Furthermore, other proteasome inhibitors also affect cardiac function (such as bortezomib or ixazomib) but this has not been studied and probably their effect has been underestimated by the fact that the duration of therapy with bortezomib is significantly shorter(2).

Homeostasis of the proteome (proteostasis) is critical for normal cellular function and thus for the overall health span of the organism. To ensure proteome stability cells have developed a complex proteome quality control, the so-called proteostasis network (PN) (3). PN is responsible for normal proteome synthesis and recycling, while in parallel it suppresses proteotoxic stress by identifying and either rescuing or degrading damaged polypeptides (4). Central role to the PN play two main proteolytic pathways, the autophagy- lysosome system (ALS) and the ubiquitin proteasome system (UPS). UPS is mainly responsible for the removal of both normal short-lived ubiquitinated proteins and of oxidized or abnormal proteins, whereas the ALS acts through degradation of long-lived proteins, aggregated ubiquitinated proteins and through recycling or damaged organelles.

The central though protein degradation mechanism in eukaryotic cells is the Ubiquitin Proteasome System. It is responsible for the non-lysosomal degradation of the majority of the intracellular proteins playing a key role in cellular processes such as regulation of cell cycle

progression, division, development and differentiation, protein quality control, apoptosis, cell trafficking, and modulation of the immune and inflammatory responses (5-6). It involves the activation, transfer, and binding of multiple moieties of ubiquitin to protein substrates by action of E1, E2, and E3 enzymes, respectively (7). Labeled by a polyubiquitin chain, proteins are recognized and degraded by the 26S proteasome complex. This complex is composed of a 20S core particle that embodies the catalytic activity and 19S regulatory particles (8).

Besides protein degradation the UPS has been attributed a significant role in the activation of various transcription factors, such as nuclear factor Kb (NF- κ B) a pivotal mediator in atherosclerosis; genes controlled by NF κ B include (among others) those that encode for vascular cell adhesion molecule-1, E-selectin, and monocyte hemoattractant protein-1. Thus UPS may play a part in maintaining a fine balance in the atherosclerotic process as a direct regulator of pro-inflammatory and/or anti-inflammatory genes and as a regulator of cell survival and proliferation (9-10).

The role of the ubiquitin-proteasome system (UPS) in vascular biology and function is under investigation with controversial results. Over the past decade, accumulating evidence supports the hypothesis of a pathophysiological role of the UPS in the process of atherosclerosis and vascular function. However, the effect of UPS on this process is not well defined. Experimental, clinical and autopsy observational studies have demonstrated that low UPS activity and increased ubiquitin conjugates are associated with unstable coronary, aortic and carotid lesions and vascular aging (11-13). However, experimental studies have yielded contradicting results about the role of UPS inhibition and atherosclerosis. Specifically, UPS inhibition induced deterioration in endothelial function of coronary arteries of hypercholesterolemic pigs and promoted an unstable plague phenotype in apolipoprotein (Apo)E deficient mice (14-15). On the other hand, UPS inhibition in human endothelial cells induced a protective stress response in endothelial cells through up-regulation of antioxidant enzyme expression and of eNOS, an enzyme with pivotal role in endothelial function, suggesting a potential anti-inflammatory and/or anti-oxidant effect (16-18). Similarly, UPS inhibition up-regulated eNOS expression and activity, which was associated with improved renal blood flow (19). Taken together, depending on the environment, dose and duration, cell type and organ studied, proteasome inhibitors can have diverse and broad effects and can act as 'poisons or remedies' in several pathophysiological processes including vascular function and atherosclerosis (20).

In order to clarify this controversial issue, the net effect of UPS inhibition on vascular function and atherosclerosis should be assessed prospectively. To the best of our knowledge, besides animal and autopsy based studies, no clinical human studies have been so far conducted in order to assess UPS inhibition on vascular function. This project will be the first to describe the acute and chronic effect of a proteasome inhibitor on vascular structure and function. Such data would 1. improve our understanding on the pathophysiological pathways linking UPS function and atherosclerosis; 2. provide therapeutic implications on the possible utility of UPS modulation in the prevention and/or treatment of atherosclerosis and 3. improve current knowledge on possible hemodynamic and vascular toxicity of carfilzomib in multiple myeloma.

2. Potential risks and benefits

This is an observational, non interventional, prospective study. Patients with relapsed or refractory multiple myeloma who have received at least one prior line of therapy and who receive carfilzomib with dexamethasone according to the approved dose and schedule (2) will be included in this observational study. No specific treatment intervention related to the study is going to be performed. No specific harms or benefits are expected due to study investigations.

3. Objectives and Purpose

The present study will assess patients with multiple myeloma receiving the proteasome inhibitor carfilzomib (CFZ), in order to investigate, *in vivo*, a wide spectrum of human atherosclerosis indices, from cardiovascular risk factors to subclinical atherosclerosis at multiple successive stages in a human model under conditions of global UPS inhibition, and correlate with cardiovascular complications associated with carfilzomib therapy, in patients receiving carfilzomib with dexamethasone.

3.1 Primary objective

• to investigate cardiovascular complications and the role of the UPS inhibition on atheromatosis and vascular function and inflammation, in patients with relapsed or refractory myeloma who are receiveing carfilzomib and dexametahsone.

3.2 Secondary objective(s)

• to outline the clinical significance of carfilzomib toxicity in hemodynamic parameters and vascular function and structure in humans

4. Study design and study end points

4.1 Description of the Study Design

The present study will assess patients with multiple myeloma receiving the proteasome inhibitor carfilzomib (CFZ), in order to investigate, *in vivo*, a wide spectrum of human atherosclerosis stages, cardiovascular risk factors and subclinical atherosclerosis at multiple successive stages in a human model under conditions of global UPS inhibition.

A. Investigation of the role of the UPS inhibition on vascular inflammation and atheromatosis

Circulating biomarkers of vascular inflammation (CRP, IL-6, ICAM-1) and vascular function (endothelial function, arterial wave reflections) and structure (intima media thickness, peripheral atheromatous plaques, plaque echogenicity and arterial stiffness) will be measured at baseline at pre-specified short and long-term time points after treatment. The acute response of vascular function and inflammatory markers to CFZ as well as long term changes in vascular structure after treatment will be assessed. These changes will be examined in comparison to the degree of change in UPS activity by validated techniques.

B. Outline of the clinical significance of carfilzomib therapy in hemodynamic parameters and vascular function and structure

In the same population and under the same design, changes in 24hour ambulatory blood pressure (BP) parameters as well as in vascular parameters as described above will be assessed focusing on time points with significant BP increments and vascular dysfunction. Subsequently, we will examine whether the magnitude of deterioration in these parameters of interest is associated with the degree of UPS activity.

5. Study enrollment and withdrawal

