6.1.3 Sample size

This is an observational study with non interventional design. Sample size calculation is made on the basis of previous data indicating that at least 2% absolute difference in Flow mediated dilatation (FMD) (corresponding to 20-30% relative difference) is considered significant and clinically relevant. With the null hypothesis being that CFZ/Dex therapy is associated with <10% relative difference in FMD and the alternative hypothesis being that a \geq 30% difference is considered as significant, and with an a=0.05, a sample of 40 patients is required for 90% power of detecting these differences (all tests are 2-sided). A dropout rate of 15% is assumed. A total number of 46 patients is thus calculated to be enrolled.

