6.5 Measurement of circulating cardiac and vascular inflammatory biomarkers

Plasma and serum samples will be obtained by venipuncture on admission and stored at - 70°C. Plasma probes will be centrifuged for 15 minutes at 10.000 g within 30 minutes of

collection. Probes will be aliquoted and stored at -70°C till analysis. The concentrations of Creactive protein, interleukin 6, vascular cell and intercellular adhesion molecule-1, E-selectin, and monocyte chemoattractant protein-1 will be measured in ethylenediaminetetraacetic acid (EDTA)-plasma at the Oncology Laboratory of the Department of Clinical Therapeutics wellcharacterized enzyme immunoassays. N-terminal pro-B-type natriuretic peptide will be measured with a sandwich immunoassay on an Elecsys 2010 instrument (Roche Diagnostics). Serum cardiac troponin T concentrations will be measured using statndard procedures.

7. Timelines of the study

Vascular measurements and blood collection will be performed at baseline before and 2 hours after dexamethasone and carfilzomib administration. These measurements will be repeated as shown below:

	Before Dexa	After Dexa	Before & after CarD	After CarD	Before & after CarD								
Time points	d -2		d0	d2	d8	d9	d15	d16	C2d1	d2	C3d1	d2	C6d1or 6 months after baseline
Vascular studies	x	X	X†	X	Xt	X	Xt	X	Xt	X	Xt	x	t x
24h ambuatory BF monitoring	×		X*		Х*				X*		X*		X*
Cardiac US	X					1				. 8			X**
Blood for Proteasome activity			x	x	x	x	X?	x	x	x			Xt
Serum collection for cardiac biomarkers	×		×t		×t		×t		×t		x		x

Schedule of assessments

* During 24th of CarD

**Only before C6d1

†2 measurements/ samples at this day

The subjects will be evaluated for AE at all visits.

8. Data presentation and statistical analysis

Data will be presented as mean ± standard deviation (SD). Continuous variables will be tested for normal distribution with the Kolmogorov-Smirnov test. Repeated measures ANOVA will be performed in order to assess significant variations of parameters of interest over time. Linear mixed models analysis will be performed in order to adjust for possible confounders over time. All tests will be two-tailed and statistical significance will be considered for P

values less than 0.05. All statistical analyses will be performed using SPSS version 21 for windows (Chicago, ILL, USA).

9. Safety reporting

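### Part B of Section 4.1 picks the visits it emphasises by their results, so the deterioration reported at those visits will be overstated

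*Protocol*

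**What the plan says.** Section 4.1 has two parts. Part A covers vascular inflammation and atheromatosis. Its measurements "will be measured at baseline at pre-specified short and long-term time points after treatment", and the changes are compared with the change in UPS activity without any filter on visits.

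Part B, whose title corresponds to the secondary objective in Section 3.2, covers 24-hour BP and the same vascular parameters. There, changes "will be assessed focusing on time points with significant BP increments and vascular dysfunction". The next sentence reads: "Subsequently, we will examine whether the magnitude of deterioration in these parameters of interest is associated with the degree of UPS activity". Part B names no visits and does not define significant.

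The only statistical criterion in the protocol is in Section 8: "All tests will be two-tailed and statistical significance will be considered for" P values below 0.05. Section 8 also plans repeated measures ANOVA over time, and linear mixed models to adjust for confounders over time. Neither is tied to the UPS question.

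**The concern.** Under Part B, a visit is emphasised because its observed change was significant. With about 40 patients, a small or moderate true change reaches significance only at visits where sampling error has added to it. The average over those visits therefore exceeds the true change, and a chance peak can qualify when there is no change at all.

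Part B is where the protocol addresses the clinical weight of carfilzomib toxicity, and its BP and vascular variables are those listed as primary endpoints in the synopsis. An overstated rise in BP would be read as a toxicity estimate. The UPS sentence follows directly and does not say which visits it uses, so an analyst could restrict it to the selected ones.

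This is not a detail left to a statistical analysis plan. The protocol itself states the rule.

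**Working it through.** **The plan's own figure.** The protocol gives no number for the Part B analysis. The nearest is Section 6.1.3: "a sample of 40 patients is required for 90% power of detecting these differences (all tests are 2-sided"), for "at least 2% absolute difference in Flow mediated dilatation (FMD) (corresponding to 20-30% relative difference"). No SD is given, so the 40 cannot be reproduced. Solving backwards for a paired comparison, the detectable standardised change is (1.960 + 1.282)/√40 = 0.513, or 0.526 with the t distribution. For a 2-point FMD change this implies an SD of change of 2/0.526 = 3.8 points. I use n = 40 below.

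**Other inputs.**
- Ambulatory BP: 5 recordings after baseline (synopsis: days 1 and 8 of cycle 1, and the start of cycles 2, 3 and 6). Section 6.2.5 lists 4.
- Vascular visits: 6 days in cycle 1, 2 each in cycles 2 and 3, and cycle 6 counted once (Section 6.2.4), which makes 11. This is a minimum.
- Assumed, because the protocol gives neither: SD of change in 24-hour systolic BP 12 mmHg, and correlation between visits 0.5. Significant is taken as two-sided P<0.05 in the direction of a rise.

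**Size of the inflation.** The standard error is 12/√40 = 1.90 mmHg. A rise is significant when it exceeds about 2.023 × 1.90 = 3.84 mmHg. Treating the SD as known, the expected mean at a selected visit with true rise δ is

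δ + SE × φ(z)/[1 − Φ(z)], where z = (3.84 − δ)/SE.

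For δ = 2, z = 0.97 and the result is 2 + 1.90 × 1.50 = 4.85. A simulation with the SD estimated (20,000 studies, 5 recordings) gives slightly lower values. The ranges below run from averaging within each study to pooling all selected visits.

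| True rise (mmHg) | Share of visits selected | Formula mean | Simulated mean | Simulated ratio to truth |
|---|---|---|---|---|
| 2 | 18% | 4.85 | 4.6–4.7 | 2.3–2.4 |
| 3 | 34% | 5.1 | 4.8–5.0 | 1.6–1.7 |
| 4 | 53% | 5.4 | 5.2–5.4 | 1.3 |
| 6 | 87% | 6.5 | 6.3–6.4 | 1.05–1.07 |

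The assumed SD matters. Averaged within each study, the ratio at a true 2 mmHg is 1.6 with an SD of 8 and 2.8 with an SD of 15. At a true 4 mmHg it is 1.05 and 1.5. In SD units, for any parameter, the ratio is about 1.9–2.0 at a true 0.2 SD, 1.4–1.5 at 0.3 SD and 1.06–1.08 at 0.5 SD. Using all visits, the estimate is unbiased (0.20 for a true 0.20).

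**False selection with no true change.** Only the adverse direction counts, so the chance per visit is 0.025.
- 5 recordings: 1 − 0.975^5 = 11.9% if visits are independent, and 9.4% by simulation at correlation 0.5.
- 11 vascular visits: 1 − 0.975^11 = 24.3% if independent, and 15.0% at correlation 0.5. Counting 12 visits gives 1 − 0.975^12 = 26.2% if independent.
- A falsely selected BP recording shows a mean rise of about 4.2–4.3 mmHg (0.36 × 12 = 4.3).

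**UPS association.** With an assumed true slope of 0.30, the average slope over selected visits is 0.26–0.30, so selection does not inflate it. With 5 visits and a true change of 0.2 SD, its standard deviation is 0.12–0.13 on selected visits, against 0.07 on all visits.

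**The case against.** - **Nothing is said to be discarded.** A reader might infer that data from other visits are thrown away. The text speaks of a focus, not an exclusion, and Section 8 keeps ANOVA and mixed models over time. This stands. What remains is that the UPS sentence leaves its visits open, and the mixed model's stated purpose is confounder adjustment.
- **The primary objective is not affected.** A reader might infer that the UPS part of the primary objective rests on visits chosen by the data. That comparison is in Part A, at pre-specified time points with no filter. This stands too.
- **The UPS association is not biased upward.** Correct; see the slope results above.
- **Significant may mean clinically significant.** It may, since Part B does not define it. The selection would still depend on the results, but the figures above would not apply.
- **The false-selection rates could be lower.** Counting changes in both directions would be wrong, because the clause concerns increments and dysfunction only. Requiring both at the same visit, or a significant overall ANOVA first, would lower the rates further. The protocol states neither requirement clearly.
- **The inflation is small if effects are large.** True: it is 6–8% at 0.5 SD, close to the 0.53 that 40 patients detect with 90% power. The protocol gives no expected BP change or SD, so smaller effects cannot be excluded.

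**Conclusion.** The concern holds in limited form. Part B writes a results-driven choice of visits into the protocol, and magnitudes reported at those visits will be biased upward. Under the stated assumptions (P<0.05, 40 patients, SD 12 mmHg, correlation 0.5), the overstatement runs from more than twofold at a true 2 mmHg rise to 5–7% at 6 mmHg. It is serious only if true effects are small to moderate. For the UPS association, the risk is lost precision, and only if the analysis is confined to selected visits. The documents do not support a claim that data are discarded, that the UPS slope is inflated, or that the primary-objective comparison is compromised. The point is worth correcting before analysis and is not fatal to the study.

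**What to change.** In Section 4.1 B, replace the focusing clause with wording that assesses changes at all scheduled time points, or name the Part B visits in advance. Report the change from baseline with a 95% CI at every scheduled visit. State in Section 8 that the UPS association is tested in the planned linear mixed model, using every visit with paired UPS and vascular or BP values. The synopsis plans UPS sampling in parallel with the vascular measurements, and the Section 7 schedule marks it at most vascular visits, so the pairs should exist. Label any summary at visits found significant as descriptive. Separating UPS activity into each patient's mean and the deviation from it is optional.

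The cost is a few sentences in two sections and slightly more modelling. It needs no new visits or samples. The price is a less striking headline change.
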